## 11.4 Exploratory Analysis

**Exploratory Objective:** Explore whether these baseline factors moderate the cessation outcomes of QuitBot, as compared

to SmokefreeTXT: (a) trust, (b) social support, (c) demographics (e.g., sex). For each moderator variable, we will calculate separate logistic regression models that will include: the moderator (Z), group assignment (X), an interaction between moderator and group assignment (X\*Z), and 30-day abstinence at 12-months post randomization as the outcome (Y). Statistically significant interactions will be assessed with plots showing how the slope of Y on X is dependent on the value of Z. The slopes will be derived from logistic regressions that correspond to the prediction of Y from X at a single value of moderator Z.

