**Study Objectives:** Conduct a randomized controlled trial of QuitBot (n = 823) versus SmokefreeTXT (n = 823), in order to determine whether QuitBot:

Objective 1. Has significantly higher 30-day point prevalence abstinence at 12 months post-randomization than SmokefreeTXT. Importance of this objective: will determine both arms' quit rates with precision and whether the QuitBot provides more robust quit rates than SmokefreeTXT.

Objective 2. Has smoking cessation outcomes significantly mediated by therapeutic alliance processes and engagement indicators in a serial multiple mediator model. Importance of this objective: will show how CAs work and identify communication processes needing further targeting. This knowledge is valuable both for CA smoking cessation interventions in particular and CA behavior change interventions in general.

Objective 3. Will be cost-effective vs. SmokefreeTXT (SFT), as measured by cost per quitter, cost per life year gained, and cost per quality-adjusted life year (QALY) gained. Importance of this objective: will provide payors and policymakers an assessment of value to inform decisions about whether to adopt QuitBot.

**Exploratory Objective:** Explore whether these baseline factors moderate the cessation outcomes of QuitBot, as compared to SmokefreeTXT: (a) trust, (b) social support, (c) demographics (e.g., sex). Importance of this objective is to identify: (1) who benefits most so that they can be provided the intervention; (2) who benefits least so that future research can explore why and determine how best to improve the intervention for them.

**Impact:** This study will advance the fields of research on CAs both for smoking cessation in particular and for health behavior change in general—regardless of whether the results are positive or null. Positive results could have high population-level impact and stimulate new lines of research into CA dissemination and implementation, and the adaptation of CAs for multiple subpopulations of smokers, languages, and community and medical settings.

Sections on Study Agent, Dose Rationale, and Other Agents have been removed as not relevant since this is not a drug trial.

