## 11.0 STATISTICAL CONSIDERATIONS

### 11.1 Study Design

We planned to enroll 1520—and actually enrolled 1647—adult daily smokers who want to quit smoking. Participants will be randomly assigned (with 0.5 probability) to (1) the QuitBot conversational agent (CA) or (2) SmokefreeTXT text messaging. Based on evidence from text messaging trials meta-analyses [1], we will stratify randomization on biological sex (male vs. female), heaviness of smoking index score ( $\leq 4$  vs  $>4$ ), and percent confidence in being smoke-free in 12 months ( $\leq 70\%$  vs.  $>70\%$ ). Moderators will be measured at baseline, mediators at 3 and 6 months post randomization, and cessation and cost-effectiveness outcomes at 3, 6, and 12 months post randomization. Random assignments will be computer-generated after consent.

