11.5 Sample Size and Power

We determined sample size for binomial proportions aimed at 80% power for Primary Objective 1 using the following parameters: (1) randomized to one of the two interventions; (2) conservative 12-month outcome survey response rate of 85%, based on our most recently published large RCT comparing two digital interventions [84]; (3) 80% completion rate of biochemical verification [103, 104]; (4) intent-to-treat analysis where, as standard in digital intervention smoking cessation trials, all those with missing data (including missing biochemical data) are coded as smokers [1, 121]; and (5) two-sided test with  $\alpha = .05$ . We adjusted all power analyses for expected non-response rates and biochemically-confirmed cessation rates so that outcomes would not be inflated.

Power for Objective 1: Objective 1 will compare 12-month quit rates between QuitBot vs. SFT. Projected quit rates at 12-month follow-up were conservatively calculated using (1) quit rates at 3-month follow-up in our pilot RCT, along with (2) well-established relapse curves, which provide a data-derived estimate (i.e., 20-35%) of the rate of decay of intervention effects by 12-month follow-up [90, 91, 122]. We estimated a relapse of 27% (between 3 and 12 month-follow-up) and survey response and biochemical verification completion rates of 85% and 80%, respectively. The 12-month quit rate for SFT is conservatively estimated as 9.3%, as consistent with the projected SFT 12-month relapse rates from the pilot RCT and the 8.4% average quit rate from the most recent meta-analyses [1, 2, 18-21]. As shown in Table 5, obtaining 80% power to significantly detect a quit rate as low as 13.9% for QuitBot (vs. 9.3% for SFT) requires 1,520 randomized participants, with 760 in each study arm.

Table 3. Objective 1 Sample Size Estimates.

	Projected relapse rate				
	20%	25%	27%	30%	35%
	QuitBot 12-month follow-up 30-day point prevalence quit rate				
	15.2%	14.3%	13.9%	13.3%	12.4%
Total in each arm	484	653	760	983	1,579
Total randomized	968	1,306	1,520	1,966	3,158

This very conservatively estimated 13.9% quit rate would have high public health impact—49% higher impact than the projected 9.3% quit rate for SFT and 65% higher than the average 8.4% quit rate observed in text messaging interventions [1, 2, 18-21].

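### The moderator analysis judges who benefits most only by an odds-ratio interaction; differences in quit rate by arm should be reported for every moderator, significant or not

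*Combined protocol and SAP*

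**What the plan says.** The Exploratory Objective in section 2.3 gives the moderator analysis a practical use. It is to identify "who benefits most so that they can be provided the intervention", and also who benefits least. It does not say whether benefit is measured as an odds ratio or as a difference in quit rates.

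Section 11.4 sets the method. For each moderator, "we will calculate separate logistic regression models that will include: the moderator (Z), group assignment (X") and their product, with 30-day abstinence at 12 months as the outcome. On follow-up it says: "Statistically significant interactions will be assessed with plots showing how the slope of Y on X is dependent on the value of Z". It adds: "The slopes will be derived from logistic regressions that correspond to the prediction of Y from X at a single value of moderator Z". Whether these slopes are drawn as log odds or as probabilities is not stated, and the section names no quit-rate difference. The moderators are trust, social support and demographics such as sex.

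Section 11.5 treats this objective as exploratory and gives it no power calculation.

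**The concern.** The product term in a logistic model has one null hypothesis: the odds ratio is the same at every value of the moderator. The decision that the objective describes, whom to offer the program, turns more naturally on how many extra people quit. The two scales agree when the control quit rate is the same at every moderator level. When it is not, a constant odds ratio implies unequal absolute gains, and a constant gain implies unequal odds ratios.

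At stake is how an exploratory result is read. A moderator with a constant odds ratio and clearly unequal gains satisfies the null and, under section 11.4, earns no plot. A moderator with equal gains can be reported as a real difference in benefit.

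**Working it through.** **Inputs from the documents.** Planned 12-month quit rates are in section 11.5: "obtaining 80% power to significantly detect a quit rate as low as 13.9% for QuitBot (vs. 9.3% for SFT"). Planned size, same section: "requires 1,520 randomized participants, with 760 in each study arm". Enrolment, section 11.1: "We planned to enroll 1520—and actually enrolled 1647—adult daily smokers who want to quit smoking". The two-sided 5% level is stated for Objective 1 and assumed here for the interaction test. Missing outcomes are coded as smoking, so the quit rates need no further inflation for dropout.

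**Assumptions.** The moderator splits the sample in half, giving 1,647 / 4 ≈ 412 per arm per level. The SmokefreeTXT quit rates by level are mine, centered on 9.3%; the documents give none.

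**The plan's own figure.** With pooled variance under the null, mean rate (0.139 + 0.093)/2 = 0.116 and difference 0.046:

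n = [1.960·√(2·0.116·0.884) + 0.8416·√(0.139·0.861 + 0.093·0.907)]² / 0.046² = 759.6, so 760 per arm. This matches section 11.5.

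The planned effect is a gain of 4.6 points, or an odds ratio of (0.139/0.861)/(0.093/0.907) = 1.574.

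**Tests compared.** With p the four cell rates and n = 412:

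- Odds-ratio interaction: z = (ln OR₁ − ln OR₂)/√Σ[1/(n·p(1−p))].
- Difference interaction: z = (gain₁ − gain₂)/√Σ[p(1−p)/n].
- Rejection probability: Φ(|z| − 1.96) + Φ(−|z| − 1.96).

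**Equal gain of 4.6 points at both levels.** Worked case, control rates 4.65% and 13.95%:

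- QuitBot rates are 9.25% and 18.55%; the odds ratios are 2.09 and 1.40.
- The log odds ratios differ by 0.397, with standard error 0.346, so z = 1.15.
- The rejection probability is 21% by formula and about 20% by simulation.

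| Control rates | Odds ratios | Odds-ratio test rejects | Difference test rejects |
|---|---|---|---|
| 7.0% vs 11.6% | 1.74, 1.47 | 8% | 5% |
| 6.0% vs 12.6% | 1.86, 1.44 | 12% | 5% |
| 4.65% vs 13.95% | 2.09, 1.40 | 20–21% | 5% |
| 3.0% vs 15.6% | 2.66, 1.37 | 38–40% | 5% |

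**Equal odds ratio of 1.574 at both levels.** Worked case, control rates 4.65% and 13.95%:

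- The gains are 2.48 and 6.38 points.
- They differ by 3.90 points, with standard error 3.09, so z = 1.26.
- The difference test has 24% power by formula and about 25% by simulation.
- The odds-ratio test sits at its null and rejects about 5% of the time.

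| Control rates | Gains (points) | Ratio of gains | Odds-ratio test rejects | Difference test rejects |
|---|---|---|---|---|
| 7.0% vs 11.6% | 3.6, 5.5 | 1.5 | 5% | 9% |
| 6.0% vs 12.6% | 3.1, 5.9 | 1.9 | 5% | 14% |
| 4.65% vs 13.95% | 2.5, 6.4 | 2.6 | 5% | 24–25% |
| 3.0% vs 15.6% | 1.6, 6.9 | 4.2 | 4–5% | 42% |

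Solving for gains exactly two-fold apart gives control rates of 5.72% and 12.88%. Their ratio is 2.25 and the gains are 3.0 and 6.0 points.

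**Power at a wider scale.** With control rates of 5% vs 15%, 80% power would need about 10,200 participants for the odds-ratio test under equal gain. The difference test under an equal odds ratio would need about 7,800.

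**The case against.** The strongest reply is that this is a choice of scale and not an error. The objective never defines benefit as extra quitters. The primary model is logistic, and section 11.5 gives detectable effects by sex as odds ratios, so an odds-ratio interaction is consistent with the rest of the plan. That stands: the scale is unstated, and the plan does not contradict itself.

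The control rates by level are also assumed. The only subgroup calculation, for sex in section 11.5, uses 9.3% for both sexes. At equal control rates both scales rank the groups alike, and at 7.0% vs 11.6% little happens. That stands too, and it limits the size of the point.

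Some absolute output is planned elsewhere. The cost-effectiveness analysis in section 11.3 divides by the difference in numbers abstinent and is repeated by sex, age, race/ethnicity and education. Sections 11.3 and 11.5 also allow results, or compare quit rates, within each sex. This partly covers the demographic moderators, but nothing equivalent exists for trust or social support.

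Finally, the sentence on slopes can be read as predicted abstinence by arm at each moderator value, which would show the absolute gap. Even on that reading, the plots are promised only for significant interactions.

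**Conclusion.** The point holds as a modest one. Section 11.4 judges moderation only by equality of odds ratios and ties its plots to significance, while the stated use leaves the scale of benefit open. If control quit rates differ by moderator level, equal gains are flagged in about 8% to 40% of trials over the range tried. Gains that differ two-fold or more can be passed over, given control rates about 2.25-fold apart. These figures rest on a half-and-half moderator and on assumed control rates.

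Three stronger readings are not supported.

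- A reader might infer that the analysis will usually flag groups with equal gain. Over the range tried, most trials would flag nothing.
- A reader might infer that it will name the wrong group as benefiting most. A reversal is arithmetically possible: odds ratios of 1.8 at a control rate of 4.65% and 1.5 at 13.95% give gains of 3.4 and 5.6 points. Nothing in the documents shows that it would arise. In one assumed case (control rates 5% and 14%, gains 4 and 6 points) the logistic test points to the lower-gain group in only about 9% of trials.
- A reader might infer that a test on the difference scale would solve the problem. At 4.65% vs 13.95% it would still miss a 2.6-fold gap in about 75% of trials.

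The sample size and the primary analysis are unaffected. This is a cheap improvement.

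**What to change.** State in section 11.4 that, for statements about who benefits most or least, benefit is the difference between arms in the 12-month quit rate.

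From the logistic models already planned, report the predicted quit rate in each arm and the difference, with 95% intervals (bootstrap or delta method). Do this at each level of every moderator, or at the quartiles of a continuous score such as trust or social support, whether or not the interaction is significant. Keep the odds-ratio interaction beside it. Plot predicted quit rates by arm for every moderator, and say that the plots are on the probability scale.

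The cost is a sentence or two in the plan and a little more analysis. The downside is two scales to report for an exploratory objective.

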11.5 Sample Size and Power

We determined sample size for binomial proportions aimed at 80% power for Primary Objective 1 using the following parameters: (1) randomized to one of the two interventions; (2) conservative 12-month outcome survey response rate of 85%, based on our most recently published large RCT comparing two digital interventions [84]; (3) 80% completion rate of biochemical verification [103, 104]; (4) intent-to-treat analysis where, as standard in digital intervention smoking cessation trials, all those with missing data (including missing biochemical data) are coded as smokers [1, 121]; and (5) two-sided test with  $\alpha = .05$ . We adjusted all power analyses for expected non-response rates and biochemically-confirmed cessation rates so that outcomes would not be inflated.

Power for Objective 1: Objective 1 will compare 12-month quit rates between QuitBot vs. SFT. Projected quit rates at 12-month follow-up were conservatively calculated using (1) quit rates at 3-month follow-up in our pilot RCT, along with (2) well-established relapse curves, which provide a data-derived estimate (i.e., 20-35%) of the rate of decay of intervention effects by 12-month follow-up [90, 91, 122]. We estimated a relapse of 27% (between 3 and 12 month-follow-up) and survey response and biochemical verification completion rates of 85% and 80%, respectively. The 12-month quit rate for SFT is conservatively estimated as 9.3%, as consistent with the projected SFT 12-month relapse rates from the pilot RCT and the 8.4% average quit rate from the most recent meta-analyses [1, 2, 18-21]. As shown in Table 5, obtaining 80% power to significantly detect a quit rate as low as 13.9% for QuitBot (vs. 9.3% for SFT) requires 1,520 randomized participants, with 760 in each study arm.

Table 3. Objective 1 Sample Size Estimates.

	Projected relapse rate				
	20%	25%	27%	30%	35%
	QuitBot 12-month follow-up 30-day point prevalence quit rate				
	15.2%	14.3%	13.9%	13.3%	12.4%
Total in each arm	484	653	760	983	1,579
Total randomized	968	1,306	1,520	1,966	3,158

This very conservatively estimated 13.9% quit rate would have high public health impact—49% higher impact than the projected 9.3% quit rate for SFT and 65% higher than the average 8.4% quit rate observed in text messaging interventions [1, 2, 18-21].

Power for Objective 2: Statistical power for testing the serial mediation of therapeutic alliance and engagement measures for smoking cessation was estimated based on the following: (1) conservative estimates of the post treatment standardized effect size for each hypothesized mediator (i.e., a small effect size of .14 [123]; (2) two-sided test with  $\alpha=.05$ ; and (3) 85% follow-up rate for mediator data collection. Conservatively, power calculations do not account for any increased power from covariate adjustment (e.g., stratified randomization factors). The PROCESS analysis method (described in Section C.7.2) uses the percentile bootstrap method to estimate the indirect effect, which provides high power while still maintaining an accurate type-I error rate [124]. For even a small three-path mediation effect (e.g.,  $0.01 \leq a_1d_{21}b_2 < 0.05$ ), according to Taylor et al. [124], a total sample size of 1,000 will attain statistical power of 99%, while power to detect larger mediation effect approaches 1. In addition, Fritz [113] showed that a sample size of 558 provides 80% power to detect small indirect effects passing through one mediator (e.g.,  $a_1b_1 = 0.02$ ). Thus, a sample size of 1,520 in this trial, with 85% follow-up, will provide high power (>99%) to detect at least small three-path and two-path mediation effects of therapeutic alliance and engagement measures.

Power for Objective 3: Statistical power is not an explicit consideration in cost-effectiveness analysis, but probabilistic sensitivity analyses will draw from model input distributions based on 95% CIs in Objective 1. Given the power in Objective 1 outcomes, we expect to obtain precise estimates of in-trial cost-effectiveness in Objective 3.

The last objective is exploratory so no power analysis was conducted.

Power for Sex as a Biological Variable: We will compare quit rates between QuitBot and SmokefreeTXT in the male and female subgroups. With 1,520 participants, and an expected ratio of 60% female:40% male, we expect to randomize 912

females and 608 males to the study. Given these sample sizes, and assuming a 9.3% 12-month quit rate for SmokefreeTXT, the minimum detectable odds ratios with 80% power are 1.78 for females and 2.00 for males.

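### The >99% power stated for mediation (Objective 2) does not follow from its stated inputs: an arm difference of 0.14 caps it at about 71% to 75%, and the path-coefficient reading ignores a binary outcome with about 12% quitters.

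*Combined protocol and SAP*

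**What the plan says.** The paragraph on power for Objective 2 (Combined protocol and SAP, section 11.5) lists its inputs: "conservative estimates of the post treatment standardized effect size for each hypothesized mediator", given as "a small effect size of .14"; a two-sided test at 0.05; and an "85% follow-up rate for mediator data collection".

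It then cites two published benchmarks. One is 99% power at a total of 1,000 for a three-path product a1·d21·b2 from 0.01 up to 0.05. The other is 80% power at 558 for a one-mediator product a1·b1 of 0.02. From these it concludes that 1,520 participants with 85% follow-up "will provide high power (>99%) to detect at least small three-path and two-path mediation effects of therapeutic alliance and engagement measures".

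Other sections fix the design to which this applies:

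- Section 11.1: two arms with assignment probability 0.5; 1,520 planned and 1,647 enrolled.
- Section 11.3: the outcome of the mediation model is 12-month cessation, so it is binary. The test is a bootstrap interval from the PROCESS macro.
- Section 11.5, Objective 1: projected quit rates of 13.9% and 9.3%, and a statement that all power analyses were adjusted for non-response and for biochemically confirmed cessation rates.
- Section 3.1.2: mediation is a secondary objective.

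**The concern.** The paragraph never says whether 0.14 is a difference between arms in standard deviations or a standardized path coefficient. It gives no value for d21 or b2. It uses no quit rate, despite the statement earlier in the same section that all power analyses were adjusted for confirmed cessation.

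The choice of scale matters. In a 1:1 trial a difference of 0.14 SD corresponds to a correlation with arm of only about 0.07, half of what a path coefficient of 0.14 implies. A rare binary outcome also carries much less information about b2 than a continuous one.

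A stated power above 99% would make a non-significant indirect effect look like strong evidence against the proposed mechanism. The plan does not say that it would be read this way, but such a figure invites it.

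**Working it through.** **Inputs.** Effect 0.14, two-sided alpha 0.05 and 85% mediator follow-up (section 11.5). Records: 0.85 × 1,520 = 1,292 planned; 0.85 × 1,647 = 1,400 on actual enrolment. Pooled quit rate: (13.9 + 9.3)/2 = 11.6%. The power of an indirect effect is approximated by joint significance, that is, the product of the power of its component paths.

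**1. Reproducing the plan's figure.** Take treatment, mediators and outcome as continuous with unit variance and put 0.14 on every path. Each path then has power Φ(0.14·√n − 1.96).

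- n = 558: Φ(3.307 − 1.96) = 0.911. Two paths: 0.911² = 83%, against 80% stated. A small percentile-bootstrap simulation (200 runs) gave about 78%, standard error about 3 points.
- n = 1,292: Φ(5.032 − 1.96) = 0.9989. Two paths: 99.8%. Three paths: 99.7%.

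So >99% reproduces on this model. The cited a1·b1 = 0.02 is also close to 0.14² = 0.0196, which suggests that 0.14 may have been meant as a path coefficient.

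**2. 0.14 as the arm difference (the plain wording).** With two equal arms the standard error of a standardized difference is √(4/n), so the a1 path has power Φ(0.14/√(4/n) − 1.96).

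- n = 1,292: Φ(2.516 − 1.96) = 71.1%.
- n = 1,400: Φ(2.619 − 1.96) = 74.5%.
- n = 1,647 (no missing mediator data): Φ(2.841 − 1.96) = 81.1%.
- For 99%: n = 4 × ((1.96 + 2.326)/0.14)² ≈ 3,750 with mediator data. At n = 1,292, a difference of about 0.24 would be needed.

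Any indirect effect containing a1 needs a1 to be detected, so 71% to 75% is a ceiling whatever d21 and b2 are. As a check, with a1 = 0.14 as an arm difference and d21 = b2 = 0.267 (so that 0.14 × 0.267² = 0.01), simulated power with a binary outcome is 71%.

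**3. Adding the binary outcome.** This step needs assumptions that the plan does not state: d21 = b2 = 0.14, with b2 on a latent logistic scale. The log odds ratio per SD is 0.14 × π/√3 = 0.254, and its standard error is 1/√(n·p·(1 − p)).

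At n = 1,292 and p = 0.116, √(1,292 × 0.116 × 0.884) = 11.51. The b2 path has power Φ(0.254 × 11.51 − 1.96) = Φ(0.963) = 83.2%.

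- Arm difference: 0.711 × 0.9989 × 0.832 = 59%.
- Correlation: 0.9989² × 0.832 = 83%.

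The two-path values agree with these to within 0.1 point. Joint-significance simulation gives 60% and 86%. A 200-run percentile-bootstrap simulation gives 50% (standard error about 3.5 points) and 88.5%, so the planned method does not rescue the lower figure.

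**4. Sensitivity (three-path power).**

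| Setting | Arm difference | Correlation |
|---|---|---|
| n = 1,292, p = 11.6% | 59% | 83% |
| n = 1,292, p = 13.6% (11.6/0.85, if non-responders are the same people) | 62% | 88% |
| n = 1,400, p = 11.6% | 64% | 86% |
| n = 1,292, p = 11.6%, 0.14 as a raw log odds ratio per SD | 26% | 36% |

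In the other direction, taking 0.14 as a correlation on every path, including the correlation with the binary outcome itself, returns to above 99%.

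**5. The cited three-path benchmark.** 0.14³ = 0.0027, below the cited minimum of 0.01; reaching 0.01 with equal paths needs 0.2154 on each. With correlations of 0.2154, two arms and 11.6% quitters, the b2 path has Φ(0.2154 × 1.814 × 11.51 − 1.96) = 99.4% and the other two paths almost 100%. Overall power is 99.4% by formula and 99.6% by simulation, about 99.5%.

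**The case against.** The strongest reply is that the sentence can be defended on the plan's own benchmark. It claims >99% for effects that are at least small, and it illustrates a small three-path effect as a product of 0.01 or more. At 0.01 from equal correlations, about 99.5% holds even with two arms and a rare binary outcome. The cited a1·b1 = 0.02 and the 558 for 80% power also fit 0.14 as a path coefficient, and on that reading the 71% cap does not arise. The cited sources that might settle the scale are not part of the documents.

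This stands as far as it goes, and it rules out two stronger readings.

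- A reader might infer that the claim fails because 0.14³ = 0.0027 lies below 0.01. It does not fail for that reason: 0.0027 still gives 99.7% in the continuous model. The gap is a mismatch between the stated input and the cited benchmark. The loss comes from the two-level treatment and the rare binary outcome.
- A reader might take 59% to 83% as the trial's mediation power. The documents do not put 0.14 on d21 or b2 and give no scale for b2. Section 11.3 writes the outcome equation additively with an error term. The 11.6% is also a rate among all randomized with missing coded as smoking, so the rate among those with mediator data may be higher.

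The objection does not rescue the figure for the input actually stated. The product of 0.01 passes only if all three paths are correlations near 0.215, whereas the plan assumes 0.14. With 0.14 as an arm difference, a product of 0.01 still has only about 71%.

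**Conclusion.** The unqualified >99% is not supported by the inputs given beside it. The firmest result is conditional on one reading: if 0.14 is the standardized arm difference in each mediator, power for any indirect effect through a1 is at most about 71% at n = 1,292 and about 75% at n = 1,400. This rests only on 1:1 allocation, 85% mediator data, two-sided 0.05 and the joint-significance argument.

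If 0.14 is a path coefficient, >99% reproduces, but for a continuous treatment and outcome that this trial does not have. The 59% and 83% show how much can be lost under one reasonable choice of d21, b2 and scale; other choices give about 26% to above 99%.

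The documents do not show that Objective 2 is underpowered on every reading. They show that its power cannot be verified, and that on the plain wording it is well below the stated figure. Mediation is a secondary objective, so the primary comparison is unaffected.

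**What to change.** In section 11.5, under power for Objective 2:

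1. Delete the unqualified >99%.
2. State whether 0.14 is a standardized arm difference or a path coefficient, and give the assumed d21 and b2 with the scale of b2.
3. Restate power for a two-arm treatment, a binary outcome at the projected quit rate and 85% mediator data. For an arm difference of 0.14 the figure can be at most about 71% (planned enrolment) to 75% (actual enrolment). Alternatively, report the smallest indirect effect that has 80% power.
4. Cite a benchmark that matches the assumed path values, or note that the 0.01 minimum does not cover 0.14 on every path.

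The change is to the power text only; design, sample size and analysis stay as they are. The cost is a less favourable stated figure, and correspondingly more caution in interpreting a null mediation result.
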